2.7 Rationale for the Current Study

There is a global pandemic caused by the SARS-CoV-2 virus, which threatens the lives of many and the economic stability of the world. Therapeutic approaches are badly needed, and an orally available, well tolerated small molecule agent could play a critical part in preventing and ameliorating COVID-19.

Evidence from non-clinical (cell culture) experiments and recently reported clinical experience in China, indicates that favipiravir may have clinical benefit in patients infected with SARS-CoV-2. Favipiravir has been shown to be active against all families of RNA viruses in which it has been tested. Clear antiviral activity (faster cessation of viral shedding) has been demonstrated in the influenza studies. Patients with influenza have recovered more quickly than placebo controls.

People who have been hospitalized to treat acute respiratory symptoms in the US have no proven option other than supportive care, which includes mechanical ventilation, oxygen therapy and treatment of co-infections and organ failure if needed. The safety profile of favipiravir is well-established. It is generally safe and well-tolerated with the exception of transient elevations of

uric acid that resolve with cessation of dosing. Thus, the risk to benefit assessment of treatment with favipiravir in the face of COVID-19 is clearly in favor of potential study subjects.

This study will assess the time course of cessation of viral shedding, and gather clinical benefit information, in patients with COVID-19 treated with favipiravir as compared to control. Data from this trial is expected to support a larger study which will demonstrate clinical benefit and serve as a pivotal trial for approval. The information gathered from this study will also help define the safety profile in this setting and enable expansion into other patient populations such as those who have been exposed but who are not yet ill. This could have a significant impact on public health.

3 DESIGN

This is an open label, randomized, controlled, multicenter Phase 2 study of favipiravir in hospitalized subjects with COVID-19. Subjects will be randomized within their study site and stratified by the severity of their disease to receive either favipiravir + standard of care (SOC) or SOC alone (See Section 9.5 for details).

SOC will be site-specific and based on what each site is currently using for COVID-19 patients.

The dose regimen will be 1800 mg favipiravir BID plus SOC or SOC alone on Day 1 followed by 1000 mg BID favipiravir (800 mg BID for subjects with Child-Pugh A liver impairment) plus SOC or SOC for the next 13 days.

The study will have 14 days of treatment and 46 days of follow-up.

4 OBJECTIVES

4.1 Primary Objective

• To determine the effect of favipiravir + SOC v. SOC on viral clearance

4.2 Secondary Objectives

- 1. To determine the clinical benefit of administering favipiravir plus SOC compared to SOC alone [assessed using a study-specified 6-point ordinal scale adapted from the WHO Master Protocol (V2.0 24FEB20) COVID-19 7-point ordinal scale] in adult patients hospitalized with COVID-19.
- 2. To determine if the treatment effect on the 6-point ordinal scale, on Day 15, is reasonably likely to reflect clinical benefit, such that it can be used as the primary clinical outcome endpoint in a similar study that is double-blinded, by assessment of the relationship of the scale to changes in clinical and symptom outcomes, including time to clinical recovery, occurrence of fever, cough, dyspnea, reduction in oxygen requirements, and other measures.
- 3. To explore the clinical effect of favipiravir + SOC v. SOC as measured by the NEWS2 system.
- 4. To determine the safety of favipiravir plus SOC compared to SOC alone, in this population.
- 5. To explore the PK of this dose regimen of favipiravir in this patient population.

5 SUBJECT POPULATION

5.1 Inclusion Criteria

All criteria must be confirmed as "YES":

- 1. Adults (18 to 80 years old):
 - a. within 72 hours of their hospitalization for infection with SARS-CoV-2, AND,
 - b. within 72 hours of the latest PCR positive result and within 7 days of the 1st PCR positive result for SARS-CoV-2. (The latest PCR could be the only PCR result.), AND,
 - c. within 10 days of onset of any COVID-19 symptoms.
- 2. Subject or their legal representative understands the requirements of the study and provides written informed consent prior to undergoing any treatment-related procedures.
- 3. If male, subject must:
 - a. Be sterile (e.g., have had a vasectomy at least 6 months prior to Day 1 dosing), OR,
 - b. Agree not to donate sperm during the study and for seven days following the last dose of study medication, AND,
 - c. Agree to strictly adhere to the following contraceptive measures during the study and for seven days following the last dose of study medication:
 - i. Abstain from sexual intercourse.
 - ii. Use a condom during sexual intercourse with a female of child-bearing potential. In addition, the female partner must use another form of contraception (e.g. intrauterine device [IUD], diaphragm with spermicide, oral contraceptives, injectable progesterone, or subdermal implants).
- 4. If female, subject must:
 - a. Be unable to bear children (have not had a period for ≥ 12 consecutive months, have had her uterus or ovaries removed, or have had a tubal ligation), OR,
 - b. Must ensure that their male partner is incapable of fathering a child (e.g., has had a vasectomy at least 6 months prior to study entry), OR,
 - c. If she is of childbearing potential will strictly adhere to the following contraceptive measures during the study and for seven days following the last dose of study medication:
 - i. Abstain from sexual intercourse, OR,
 - ii. Must ensure that her male partner agrees to use a condom during sexual intercourse and agree to use an approved method of contraception (e.g., IUD, diaphragm with spermicide, oral contraceptives, injectable progesterone, or subdermal implants).
 - d. Agrees to stop breast-feeding prior to first dose of study drug and through seven days after completing therapy.
 - e. Has a negative pregnancy test at screening.
 - f. Has not had unprotected sexual intercourse within the past month.

- 12. Is on another antiviral or is participating in a clinical trial for the treatment of COVID-19.
- 13. Is on a ventilator at the time of study entry.
- 14. Is deemed by the Investigator to be ineligible for any reason.

5.3 Removal of Subjects from Treatment

The participation of a subject in the study or the administration of treatment may be terminated at any time for one of the following reasons:

- The subject desires to discontinue study treatment.
- The subject withdraws consent to participate in the study.
- The subject is unwilling or unable to comply with the safety procedures.
- The subject is discovered to be pregnant.
- The subject experiences a medical emergency that necessitates withdrawal.
- The subject is withdrawn at the discretion of the Investigator for medical reasons or non-compliance.

5.4 Individual Stopping Rule

In addition to the above, a. subject should be removed from favipiravir treatment if one of the following criteria is met:

- AST or ALT $> 8 \times ULN$
- ALT or AST > 3 × ULN AND total bilirubin > 2 × ULN
- AST or ALT $> 3 \times ULN$ AND patient has right upper quadrant pain or eosinophilia
- Uric acid > 20mg/dL

A subject whose treatment is terminated should remain in the study for appropriate follow up assessments.

6 STUDY TREATMENT - FAVIPIRAVIR

6.1 Study Drug

Favipiravir will be provided in 200 mg tablet form to be stored at controlled room temperature (15°C to 30°C [59°F to 86°F]) and shielded from light.

6.2 Standard Dose

Subjects randomized to the favipiravir + SOC arm will be administered loading doses of 1800 mg BID (Ideally 12 hours apart but 10–16 hours is allowed) on Day 1, and then maintenance dosing of 1000 mg twice daily BID (Ideally 12 hours apart but 10–16 hours is allowed) on Days 2–14 beginning 24 hours after the first dose. Day 1 is deemed to be the first 24 hours after enrollment into the study, with time 0 (time of first dose) occurring as soon as possible after the subject's eligibility has been confirmed.

An exception to the above maintenance dose will be made for those subjects entering the study with a Child-Pugh liver impairment of grade A who will receive favipiravir 800 mg BID on Days 2 through 14.

6.3 Administration of Favipiravir

Favipiravir is provided as 200 mg tablets and dosed orally. Favipiravir is rapidly and completely absorbed after oral administration of the 200 mg immediate release tablets.

If a subject cannot swallow the tablets, a slurry may be administered by nasogastric (NG) or orogastric (OG) tube. (Instructions for preparing the slurry are provided in the pharmacy instructions.). If an NG or OG tube cannot be placed, the favipiravir tablets can be crushed and administered in a "masking" substance such as apple sauce or cranberry juice.

Subjects who vomit during or immediately after dosing, should not be re-dosed.

The Investigator must consult with the Sponsor Medical Monitor prior to adjusting the dose level, regimen, or route of dosing.

6.3.1 Outpatient Favipiravir Dosing

It is possible that some subjects may improve sufficiently to be discharged from the hospital prior to Day 14. If this happens, subjects in the favipiravir + SOC arm, will be dispensed sufficient favipiravir to ensure continued dosing until their next study visit. Subjects will also be given a Diary Card to record the date and time they take their dose.

Subjects will also be instructed that if they miss a dose, they should follow the guidelines:

- 1) If more than 1/2 the time until their next dose has elapsed, they SHOULD NOT take the dose. They should just take the next dose at the normal scheduled time.
- 2) If less than 1/2 the time until their next dose has elapsed, they should take the missed dose immediately.
- 3) In both cases, they should then return to their regular dosing schedule.

6.4 Drug Accountability

The Investigator must maintain adequate records showing the receipt, dispensation, or other disposition of favipiravir including the date, quantity, and identification of subjects (study ID) who received favipiravir. Drug supplies will be inventoried and accounted. Unused supplies of all favipiravir will be returned to the Sponsor or destroyed on site in accordance with local procedures upon approval of the Sponsor.

6.5 Treatment Compliance

All doses of study drug will be administered by site staff while in the hospital. If the patient is discharged while still on drug, the pharmacy will provide bottles of favipiravir for outpatient use (Exact dispensing instructions for outpatients will be described in the pharmacy instructions). Assessment for compliance with each dose will be monitored and recorded in accordance with site standard operating procedures.

6.6 Treatment Precautions

An overdose is defined as any dose of study drug given to a subject or taken by a subject that exceeds the dose described in this document. In the event of an overdose, the subject should be treated symptomatically, and the Sponsor informed.

6.7 Prohibited Concomitant Therapy

The following may interact with favipiravir and risks and benefits should be carefully considered prior to treatment with the following:

- Any other anti-viral medication whether investigational or approved.
- Any drugs known to significantly inhibit AO activity (e.g., pyrazinamide, amitriptyline, chlorpromazine, clomipramine, clozapine, erythromycin, ketoconazole, nortriptyline,

quetiapine, raloxifene, perphenazine, promethazine, propafenone, tamoxifen, thioridazine).

- Any drugs metabolized by the AO pathway (e.g., famciclovir, hydralazine, lamivudine, sulindac, zaleplon, ziprasidone).
- Drugs with possible drug-drug interactions (concomitant medications requiring particular attention see the Investigator Brochure).

For hospitalized subjects on the favipiravir + SOC arm, site staff will be reminded to consider the above prior to prescribing concomitant medications.

The following message appears on the Diary Card given to subjects that are discharged with favipiravir to take at home (see Section 6.3.1):

Favipiravir can slightly increase the concentration of acetaminophen (Tylenol) in the blood. Do not take more than 3000 mg (do not forget to include any acetaminophen that could be in over-the-counter preparations) in a 24-hour period as long as you are taking favipiravir.

There are possible interactions of favipiravir with other drugs. During the time that you remain on favipiravir, do not take any medications or supplements that you were not taking while you were in the hospital, without getting approval first from the study doctor.

Favipiravir can cause you to be mildly sensitive to sunlight. Please avoid excessive exposure to sunlight or artificial ultraviolet light (tanning machines) while you are on favipiravir.

7 STUDY PROCEDURES

Refer also to Section 13: Schedule of Assessments

7.1 Day 1 (PRE-DOSE)

- Obtain informed consent.
- Verify eligibility per the inclusion and exclusion criteria. (See Sections 5.1 and 5.2)
 - o Review and record medical history, including tobacco use, to ensure there are no exclusionary illnesses.
 - Review and record concomitant medications for possible prohibited medications. (See Section 6.7)
- If subject is female of child-bearing potential and meets inclusion criteria 4.c, obtain urine or blood pregnancy test and proceed it result is negative.
- Measure and record vital signs (BP, HR, Temp, Resp).
 - **NOTE:** vital signs to be recorded and entered in the EDC every day while subject is in the hospital and on return study visits after discharge.
- Perform Physical exam (may be done by the Principal Investigator or their designee)
- Assess and record baseline clinical status according to the following study-specific 6-point scale:
 - 1. Not hospitalized
 - 2. Hospitalized, not requiring supplemental oxygen
 - 3. Hospitalized, requiring supplemental oxygen
 - 4. Hospitalized, on non-invasive ventilation or high flow oxygen devices
 - 5. Hospitalized, on invasive mechanical ventilation or ECMO

6. Death

NOTE: Clinical Status to be recorded and entered in the EDC every day while subject is in the hospital and on return study visits after discharge.

- Assess and record NEWS2 (See charts by clicking this link: https://www.rcplondon.ac.uk/projects/outputs/national-early-warning-score-news-2
 - **NOTE:** NEWS2 assessment to be recorded and entered in the EDC every day while subject is in the hospital and on return study visits after discharge.
- Assess and record ECOG Performance Status and Study-specific Symptom Status (see Appendix A).
 - **NOTE:** ECOG Performance Status and Study-specific Symptom Status to be collected and recorded every day while the subject is in the hospital and on return study visits after discharge.
- Collect nasopharyngeal and oropharyngeal swabs for virologic testing. (See Virology Laboratory Manual.)
- Collect blood samples for:
 - o Antibodies to SARS-CoV-2.
 - o Hematology and clinical chemistry laboratory analyses
- Collect and record SpO2 by Finger Sensor
 - **NOTE:** SpO2 to be recorded and entered in the EDC every day while subject is in the hospital and on return study visits after discharge.
- Perform subject randomization (via EDC) to establish treatment arm (favipiravir + SOC or SOC alone).
- For subjects randomized to favipiravir: Collect blood sample for PK prior to first dose (refer to PK laboratory manual for handling and shipping instructions).

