13 SCHEDULE OF ASSESSMENTS

ASSESSMENT	HOSPITALIZED							FOLLOW UP Outpatient or Hospitalized		
	DAY 1 PRE-DOSE	DAY 1 POST-DOSE	DAY 2	DAY 3	DAY 8	Day 11	DAY 14	DAY 15 (-1 to + up to 2 days)	DAY 29 ± 2 days	DAYS 45 and 60 ± 2 days ⁸
Informed Consent	X							• /		·
Medical/Surgical History	X									
Physical Exam 10	X									
Limited Physical Exam ³		X	X	X	X	X	X	X	X	X
Concomitant Medications Review ¹²	X		X	X	X	X	X	X	X	X
Review of Entry Criteria	X									
Vital Signs (BP, HR, Temp, Resp) ³	X	X	X	X	X	X	X	X	X	X
Clinical Laboratory Exams ^{1,2,,9}	X			X	X	X		X	X	
Blood for antibodies to SARS-CoV-2	X							X	X	
Blood for PK Sampling	X ⁴	X^4	X^5	X^6	X^5	X^6	X^5			
SpO2 by Finger Sensor ³	X	X	X	X	X	X	X	X	X	X
Urine or Blood Pregnancy Test	X									
Nasopharyngeal and Oropharyngeal Swabs for Viral RNA, PCR and TCID ₅₀	X			X ¹¹	X ¹¹	X ¹¹		X	X	
Clinical Status – 6-point Ordinal Scale ³	X		X	X	X	X		X	X	X
National Early Warning Score (NEWS2) ³	X		X	X	X	X		X	X	X

	DAY 1 PRE-DOSE	DAY 1 POST-DOSE	DAY 2	DAY 3	DAY 8	Day 11	DAY 14	DAY 15 (-1 to + up to 2 days)	DAY 29 ± 2 days	DAYS 45 and 60 ± 2 days ⁸
ECOG Performance Status ³	X		X	X	X	X	X	X	X	X
Study Specific Symptom Status ³	X		X	X	X	X	X	X	X	X
Randomization	X									
Investigational Product Dosing		Favipiravir Dosing Days 1-14 (1800 mg BID on Day 1000 mg BID Days 2-14) ⁷								
Solicitation of Treatment- Emergent Adverse Events ³		X	X	X	X	X	X	X	X	X
Release from the Study										X

- 1. Hematology, Chemistry (See Section 8.4).
- 2. May use results of labs taken at the hospital as part of SOC if done no more than 24 hours prior.
- 3. To be measured every day while hospitalized and at each clinic visit after hospital discharge through Day 60
 - a. Vital signs
 - b. Clinical Status 6-point scale
 - c. NEWS2
 - d. ECOG Performance status
 - e. Study-specific symptom status
 - f. Adverse Events
 - g. SpO2
 - h. Limited PE (heart and lungs)
- 4. PK on Day 1 prior to favipiravir dosing and between 45 to 75 minutes post-first dose.
- 5. PK trough samples to be taken approximately 30 minutes prior to any dose.
- 6. PK peak samples to be taken between 45 to 75 minutes post-dose
- 7. Maintenance dose for CP score A is 800 mg BID.
- 8. Days 45 and 60 may be completed in the hospital, outpatient clinic, or by phone
- 9. Subjects will undergo 9 planned venipunctures.
- 10. To be completed by PI or designee

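### The Day 1 pregnancy-test instruction in Protocol 7.1 covers only women entering under inclusion 4.c and omits a woman of child-bearing potential who enters under 4.b alone

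*Protocol*

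**What the plan says.** Inclusion criterion 4 (Protocol Section 5.1, with the same content in the Synopsis) gives a female subject three alternative routes, joined by OR:

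- 4.a: she is unable to bear children.
- 4.b: "Must ensure that their male partner is incapable of fathering a child".
- 4.c: "If she is of childbearing potential will strictly adhere to the following contraceptive measures during the study", meaning abstinence, or a condom plus an approved method.

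Items 4.d to 4.f follow at the same lettering level. Item 4.e reads "Has a negative pregnancy test at screening" and names no route.

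Section 7.1 (Day 1, pre-dose) first instructs the site: "Verify eligibility per the inclusion and exclusion criteria". A later bullet in the same list orders the test: "If subject is female of child-bearing potential and meets inclusion criteria 4.c, obtain urine or blood pregnancy test". That bullet makes proceeding depend on a negative result.

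Section 7 opens with "Refer also to Section 13: Schedule of Assessments". There, the row "Urine or Blood Pregnancy Test" is marked at Day 1 pre-dose with no footnote limiting it to 4.c. SAP Table 1-1 reproduces the row in the same form.

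**The concern.** Section 7.1 is the list a site works through on Day 1, and its pregnancy-test bullet is the only text that tells staff which women to test. It sets two joint conditions: child-bearing potential, and meeting 4.c. A fertile woman who qualifies through her partner's sterility and gives no 4.c undertaking satisfies the first condition but not the second. A site relying on that bullet could randomize and dose her untested, in breach of 4.e.

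This is a patient-safety matter. Section 2.2 advises against favipiravir in women who are or may become pregnant, citing embryo-fetal toxicity studies. Day 1 pre-dose is the only scheduled pregnancy test, so no later scheduled test would pick up a missed one.

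**Working it through.** The plan states no figure on this point, so the check is a comparison of texts.

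**Who is tested, by route**

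| Route | Can she bear children? | 4.e as written | 7.1 bullet | Section 13 row |
|---|---|---|---|---|
| 4.a | No | Test | No test | Test |
| 4.b alone | She may | Test | No test | Test |
| 4.c | Yes | Test | Test | Test |

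The 7.1 bullet is the text out of line. The 4.a difference carries no safety weight, because those women cannot be pregnant. The 4.b difference does.

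**Is the 4.b group real?** A woman who cannot bear children already qualifies under 4.a, so 4.b matters mainly for women who can. Because the routes are joined by OR, meeting 4.b removes any need to meet 4.c. Two routes are therefore open to women of child-bearing potential (4.b and 4.c); the bullet names one and omits one.

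**What still requires the test for her?** Four provisions: 4.e itself, since all inclusion criteria must be confirmed; the eligibility check in 7.1; the schedule to which Section 7 refers; and Sections 6.2 and 7.2, which place the first dose after "eligibility has been confirmed". The bullet does not exempt her from any of these.

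**Where the wording probably came from.** 4.c is the only lettered item under criterion 4 that names childbearing potential, so the reference may have been meant as a pointer to that group. As written, however, it is a second condition added to child-bearing potential.

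**How many women?** The documents give no share entering on 4.b alone. Assume 0%, 5% or 10% of about 50 subjects, randomized 1:1:

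- women entering on 4.b alone = 50 × share = 0, 2.5, 5
- expected on favipiravir = that number × 0.5 = 0, 1.25, 2.5

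These count women whom the bullet would not reach. They do not count missed pregnancies, which would be far fewer.

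**The case against.** The strongest reply is that the test is already required. 4.e must be answered yes, the eligibility check appears earlier in the same list, and the schedule row has no restriction. For harm to occur, a site would have to follow one bullet, pass over the eligibility check and record 4.e as met with no test. Pregnancy is also unlikely in this group: the partner is incapable of fathering a child, 4.f excludes unprotected intercourse in the past month, and Section 5.3 lists discovered pregnancy as a reason to end treatment. All of this stands, and it is why the risk is rated low. The safeguards are not complete, though. 4.b describes the partner and does not establish that she is not pregnant now; 4.f looks back only one month; and stopping on discovery comes after any exposure. Since the 7.1 bullet already leaves out 4.a women whom 4.e literally covers, a site could reasonably take 4.e as not applicable to a 4.b woman too.

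A second reply is that no connector joins 4.c to items 4.d to 4.f, so 4.e might attach to 4.c alone, in which case 7.1 would agree with it. That reading is possible but weaker. 4.e is lettered at the same level as the three routes, and the schedule row carries no such limit. Even on that reading, 7.1 and the schedule would disagree on whom to test.

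A third is that the proposed wording would still be narrower than a literal 4.e, because 4.a women would remain outside it. This is true, and it has no safety consequence.

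**Conclusion.** The concern holds. The 7.1 bullet is narrower than 4.e and the schedule, and it leaves out a woman of child-bearing potential who enters on 4.b alone. It is an incomplete instruction: the requirement to test her exists elsewhere in the protocol and nothing withdraws it.

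The safety risk is low and the number affected may be zero. The range of 0 to 5 women, with 0 to 2.5 expected on favipiravir, rests wholly on the assumed 0% to 10% share. The conclusion about the wording does not depend on that range. It rests on reading 4.e as applying across the routes, which the lettering and the schedule support. The design and the statistical analysis are unaffected. The point should be fixed because the bullet is wrong as an operational rule, bears on fetal exposure and is easily corrected.

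**What to change.** In Section 7.1, delete the second condition, the one referring to 4.c. The bullet then orders a urine or blood pregnancy test for any female subject of child-bearing potential and lets the site proceed only on a negative result. This covers entry under 4.b and 4.c alike, before randomization.

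Leave 4.e and 4.f as they are, add no exemption for 4.a women, and make no change to Section 13 or SAP Table 1-1, whose rows are already unrestricted.

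The cost is one phrase removed in one place and, under the assumption above, 0 to 5 tests that are already in the Day 1 pre-dose schedule.
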